## **Pre-Flare Treatment Period**

The analysis phase as described below is applicable to safety analyses only of the pre-flare treatment period.

Table 6.1: 2 Flow chart of analysis phases for pre-flare treatment period

Study analysis phase	Description	Start (included)	End (included)
Screening  phase	Screening	Earliest of (Date of informed consent, first screening procedure)	Date/time of injection of first maintenance study drug minus 1 minute
Maintenance treatment phase & Residual effects period	Maintenance on-treatment period	Date/time of injection of first maintenance study drug (Day 1 for maintenance)	Without flare treatment: Date of injection of last maintenance study drug + 112 days at 11:59 p.m. With flare treatment: Date/time of infusion of first flare study drug minus 1 minutes
Follow-up  phase	Off-treatment period	Without flare treatment: Date of injection of last maintenance study drug + 113 days at 12:00 a.m.	Latest of: i) Date of EOS visit (Week 352 visit); ii) last contact date on End of Study page at 11:59 p.m.

Dates are defined individually per patient. If more than one date is associated with a specific visit, measurements associated with a specific date are assigned to a study analysis phase according to the rules specified in the table. An analysis phase will not extend beyond the start date of the following phase.

 The off-treatment period (i.e. Follow-up phase) only exists if the trial completion date is after the date of end of last injection + 112 days.

 The screening phase does not exist for re-induction treated patients who subsequently receive maintenance treatment.

 Safety data is censored for reporting following intake of disease flare treatment with spesolimab. Measurements collected with date only on the day of first flare treatment are assigned to the pre-flare treatment period.

Assessments done on the same day as the first maintenance treatment dose will be assigned to a study analysis phase based on assessment via date and time. If time is not collected for a particular assessment, then assignment will be to the previous study analysis phase, i.e. to the screening phase for patients who directly enter the trial into the maintenance period, or to the re-induction phase for patients who directly enter the trial into the re-induction period.

For all subjects who received disease flare treatment with spesolimab during the maintenance period, safety assessments (including adverse events, laboratories, vital signs etc.) which occurred subsequent to such intake will be excluded from presentations according to the actual treatments in a primary approach.

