## **Post-Flare Treatment Period**

The analysis phase as described below is applicable to safety analyses only of the post-flare treatment period.

For the post-flare treatment period of the maintenance period, the analysis phases described below consider the inclusion of data from the following study parts: disease flare treatment with 1200 mg spesolimab single i.v. infusion followed by intensified maintenance dosing with 600 mg s.c. spesolimab q6w, up to the (extended) REP from the last dose of spesolimab (either injection or infusion).

Table 6.1: 3 Flow chart of analysis phases for the post-flare treatment period

Study analysis phase	Description	Start (included)	End (included)
Post-flare treatment phase & Residual effects period	Post-flare treatment period (REP extended)	Date/time of infusion of first flare study drug (Day 1)	Date of end of (infusion or injection) of last administered spesolimab + 112 days at 23:59
Follow-up  phase	Off-treatment period (REP extended)	Date of end of (infusion or injection) of last administered spesolimab + 113 days at 12:00 a.m.	Latest of: i) Date of End-of-Study visit; ii) last contact date on End of Study page at 23:59

Dates are defined individually per patient. If more than one date is associated with a specific visit, measurements associated with a specific date are assigned to a study analysis phase according to the rules specified in the table. An analysis phase will not extend beyond the start date of the following phase.

 The off-treatment period (i.e. Follow-up phase) only exists if the trial completion date is after the date of end of last infusion or injection + 112 days.

The post-flare treatment period only applies to those patients who are administered a disease flare treatment with spesolimab. Assessments done on the same day as the first disease flare treatment dose will be assigned to a study analysis phase based on assessment via date and time. If time is not collected for a particular assessment, then assignment will be to the previous study analysis phase, i.e. to the pre-flare treatment period.

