### **Disease Flare Treatment Period**

The analysis phase as described below is applicable to both the efficacy and safety analyses of the disease flare treatment period.

The following phases will be used for assessment on the efficacy and AE safety profile only in patients who take disease flare treatment with 1200 mg spesolimab single i.v. infusion. This analysis phase considers the fixed 12-week duration after administration of a disease flare spesolimab infusion up to the time of the planned endoscopy measurement (Rx-Week 12 defined in [Table 6.7: 3](#)).

Table 6.1: 5 Flow chart of analysis phases for disease flare treatment period

Study analysis phase	Description	Start (included)	End (included)
Disease flare treatment phase*	On-treatment period after flare infusion with spesolimab	Date/time of start of infusion of flare treatment (Day 1 for flare treatment)	Date of end of infusion of flare treatment + 98 days at 23:59

Dates are defined individually per patient. If more than one date is associated with a specific visit, measurements associated with a specific date are assigned to a study analysis phase according to the rules specified in the table. An analysis phase will not extend beyond the start date of the following phase.

\*One patient may have multiple disease flare treatment phases if multiple flares happen at different times.

The disease flare treatment period only applies to those patients who are administered a disease flare treatment with spesolimab. Assessments done on the same day as the first disease flare treatment dose will be assigned to a study analysis phase based on assessment via date and time. If time is not collected for a particular assessment, then assignment will be

to the previous study analysis phase, i.e. to the pre-flare treatment period for first administration of disease flare treatment, or to the post-flare treatment period for subsequent administrations.

The selection of data for presentation in this analysis is described in Tables about time window in [Section 6.7](#). Treatments will be labelled as follows:

- “Re-induction Speso 1200 mg IV q4w” [applicable to the re-induction period]  
Selected tables also by prior parent trial treatment
- “Pre-Flare SC” [applicable to the pre-flare treatment period, i.e., censoring data after intake of first flare treatment, including also the old dosing schedule]

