#### 7.8.1 Adverse events

AEs will be coded with the most recent version of MedDRA.

The analyses of AEs will be descriptive in nature. All analyses of AEs will be based on the number of patients with AEs and not on the number of AEs. System organ classes (if applicable) will be sorted according to the standard sort order specified by the EMA, preferred terms (if applicable) will be sorted by total frequency (within system organ class).

For further details on summarization of AE data, please refer to "Handling and summarization of adverse event data for clinical trial reports and integrated summaries" ([4](#)) [*KM Asset BI-KMED-BDS-HTG-0041*] and "Handling of missing and incomplete AE dates" ([3](#)) [*KM Asset BI-KMED-BDS-HTG-0035*].

The analysis of AEs will be based on the concept of treatment emergent AEs. This means that all AEs will be assigned to the screening phase, re-induction on-treatment period (i.e. re-induction treatment phase plus REP), maintenance on-treatment period (i.e. maintenance treatment phase plus REP) or off-treatment period (i.e. follow-up) as defined in [Section 6.1](#). Adverse events occurring in the maintenance and re-induction periods will be separately described. Since only the start date of an AE is collected (without start time), any AE occurrence on the same day as the first re-induction or first maintenance spesolimab administration will be assigned to the respective on-treatment period. For patients who switch directly to maintenance treatment at week 12 of the re-induction period, adverse events occurring on this first day of maintenance treatment will be included in summaries of the maintenance period only. Exposure-adjusted adverse event incidence rates (per the primary endpoint) will be calculated using the following approach:

- 1) The exposure adjusted incidence rate (per 100 subject years) of a selected treatment emergent adverse event is defined as the number of subjects experiencing the adverse event per treatment group during time at risk divided by the total time of subjects at risk in that treatment group to contribute the event to the analysis multiplied by 100 (per 100 subject years), where:
  - 2) Time at risk [subject years] = (date of onset of AE – study drug start date + 1) / 365.25

For safety analysis on the post-flare treatment periods: Time at risk [subject years] = (date of onset of AE – first i.v. disease flare treatment start date + 1) / 365.25

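### An adverse event starting on the day of the first i.v. flare infusion is assigned to the s.c. pre-flare tables and left out of both flare tables

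*SAP*

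**What the plan says.** SAP 6.1 states the date-only default for the flare boundary in three places.

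- Pre-flare period, Table 6.1:2 footnote 3: "Measurements collected with date only on the day of first flare treatment are assigned to the pre-flare treatment period".
- Post-flare period, where no time is collected: "then assignment will be to the previous study analysis phase, i.e. to the pre-flare treatment period".
- Disease flare period: date-only items go "to the pre-flare treatment period for first administration of disease flare treatment, or to the post-flare treatment period for subsequent administrations".

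SAP 7.8.1 assigns AEs to the phases of Section 6.1 and then makes an exception for same-day AEs. The exception opens with "Since only the start date of an AE is collected (without start time), any AE occurrence on the same day as the first re-induction", and it goes on to name the initial maintenance dose as well; an AE on either day counts in the period which that dose opens. Flare infusions are not named.

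Other text in 6.1 points the opposite way. The first sentence of footnote 3 reads "Safety data is censored for reporting following intake of disease flare treatment with spesolimab". The paragraph after Table 6.1:2 says that, for patients given flare treatment, "safety assessments (including adverse events, laboratories, vital signs etc.) which occurred subsequent to such intake will be excluded" from the primary presentation. Protocol 7.3.4 says the same in substance. Table 6.1:1 footnote 2 refers to AEs with both date and time collected, which does not fit the statement in 7.8.1.

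**The concern.** The flare-specific tables exist to separate what happens after a 1200 mg i.v. infusion from what happens on s.c. maintenance. The AEs most clearly tied to an infusion are those that begin on the infusion day. SAP 7.8.1 lists infusion reactions, including anaphylactic reaction, as AEs of special interest, and Protocol 5.2.2 requires hypersensitivity monitoring for one hour after i.v. dosing. Infusion-day onset is therefore a case the trial anticipates.

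Under the stated rules, such a reaction to the first flare infusion appears under an s.c. label and disappears from the i.v. label. For a term that occurs only on the day of that infusion, the Disease Flare rate would be zero whatever the true count.

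**Working it through.** The SAP gives no figure to reproduce here. The check traces the assignment rules and then applies the SAP's time-at-risk formula to one event.

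**Does the 6.1 default reach AEs?** Three parts of the SAP say it does.

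1. The exclusion paragraph after Table 6.1:2 lists AEs among safety assessments.
2. The disease flare phase, which carries the default, is defined for "assessment on the efficacy and AE safety profile only in patients who take disease flare treatment".
3. Section 6.1 gives the same default for the first re-induction and first maintenance doses, and 7.8.1 reverses it for AEs at exactly those two doses. The reversal would be unnecessary if the default did not cover AEs.

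**Where does an AE go if it starts after the infusion on the same day?**

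| Case | Assigned to |
|---|---|
| First flare, date only (SAP as written) | Pre-flare; neither flare period |
| Second or later flare, date only | Post-flare, but not that infusion's disease flare period |
| Any flare, start time known | Post-flare and disease flare |
| Any flare, date only, 7.8.1 rule extended | Post-flare and disease flare |

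**Effect per event.** The inputs are:

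- time at risk = (onset − period start + 1)/365.25 for a patient with the event (SAP 7.8.1), with censoring at the end of the period otherwise;
- the disease flare period ends 98 days after the infusion (Table 6.1:5);
- the post-flare period ends 112 days after the last spesolimab dose (Table 6.1:3);
- the pre-flare period ends one minute before the first flare infusion (Table 6.1:2).

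The figures assume that the patient has no other occurrence of the same term in the period concerned, and that death or an interim cut-off does not shorten follow-up.

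- Event counted on day 1 of either flare period: (0 + 1)/365.25 = 0.0027 years.
- Disease Flare with the event lost: (98 + 1)/365.25 = 0.271 years. The patient changes from 1 event in 0.0027 years to 0 events in up to 0.271 years.
- Post-Flare at the first flare with the event lost, taking the shortest case where the infusion is the last dose: (112 + 1)/365.25 = 0.309 years. The patient changes from 1 event in 0.0027 years to 0 events in at least 0.309 years.
- Pre-Flare SC: the period ends on the infusion date, so time at risk does not change and the term gains 1 event.

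**Illustration on assumed counts only.** Suppose 10 to 40 patients receive flare treatment, 1 to 3 of them have a given event on the infusion day only, and the rest are followed for 99 days. With the extended rule, the Disease Flare rate per 100 subject-years runs from 100 × 1/[(39 × 99 + 1)/365.25] = 9.5 (1 of 40) to 100 × 3/[(7 × 99 + 3)/365.25] = 157.4 (3 of 10). Under the rule as written it is 0 in every case.

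**The case against.** The best reply is that this is an oversight which the surrounding text resolves. Footnote 3 speaks of measurements, and SAP 6.7 uses that word for laboratory, vital sign, efficacy and biomarker data while treating AEs separately. The censoring statements, the Pre-Flare SC label and the start of both flare phases at the infusion date and time all show that a post-infusion AE is meant to be a flare-period event. The time-at-risk formulas also allow one day at risk for a same-day onset. If AE start time is collected, as Table 6.1:1 footnote 2 suggests, the event is placed correctly. Internal AE guidances cited in 7.8.1, and SAP sections absent from the public text (5.4, 6.4, 9), might contain the missing rule.

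The effect is also limited. The trial is descriptive, and the event stays on-treatment whichever way it is assigned. Protocol 3.3.4.1 withdraws patients after more than one confirmed flare, so the later-infusion case should be rare.

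Much of this stands as a limit on size and on intent, but it does not supply a rule. If the default does not cover AEs, nothing in 6.1 or 7.8.1 places a date-only AE against a boundary set to the minute, although SAP 7.8 requires AE tables for all three flare-related periods. That the event stays on-treatment is not decisive either. At the switch from re-induction to maintenance a same-day AE is also on-treatment both ways, and 7.8.1 still assigns it to the new period.

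**Conclusion.** The concern holds. As written, the SAP places an AE that follows the first flare infusion on the same day under Pre-Flare SC and outside both flare tables, against its own censoring text. At later flare infusions the event stays in Post-Flare but is lost from that flare's Disease Flare period.

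The damage is confined to the flare-split AE tables, mainly at the level of AEs of special interest and preferred terms. The count of patients with any treatment-emergent AE may not change, because a flare patient may already have had one before the flare. Overall Maintenance tables, re-induction tables and individual listings are unaffected, and an AE that begins before the infusion that day is correctly pre-flare.

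The total size cannot be stated, since the documents give neither a same-day reaction rate nor a count of flare infusions. The conclusion rests on 7.8.1 being right that AE start time is not collected, and on no overriding rule existing in material that is not public.

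**What to change.** 1. In SAP 7.8.1, extend the same-day AE rule to every flare infusion: an AE with onset on the infusion date belongs to the post-flare period and to that flare's disease flare period.
2. In SAP 6.1, limit the date-only default to laboratory values, vital signs and other pre-dose measurements.
3. Check Table 6.1:1 footnote 2 and 7.8.1 against the eCRF and make them agree. If AE start time is in fact recorded, use it.

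The cost is a few lines of SAP text and one derivation line. The downside is that an AE which began earlier on the infusion day will be attributed to the infusion. The SAP already accepts that for the first re-induction and first maintenance doses.

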## **Post-Flare Treatment Period**

The analysis phase as described below is applicable to safety analyses only of the post-flare treatment period.

For the post-flare treatment period of the maintenance period, the analysis phases described below consider the inclusion of data from the following study parts: disease flare treatment with 1200 mg spesolimab single i.v. infusion followed by intensified maintenance dosing with 600 mg s.c. spesolimab q6w, up to the (extended) REP from the last dose of spesolimab (either injection or infusion).

Table 6.1: 3 Flow chart of analysis phases for the post-flare treatment period

Study analysis phase	Description	Start (included)	End (included)
Post-flare treatment phase & Residual effects period	Post-flare treatment period (REP extended)	Date/time of infusion of first flare study drug (Day 1)	Date of end of (infusion or injection) of last administered spesolimab + 112 days at 23:59
Follow-up  phase	Off-treatment period (REP extended)	Date of end of (infusion or injection) of last administered spesolimab + 113 days at 12:00 a.m.	Latest of: i) Date of End-of-Study visit; ii) last contact date on End of Study page at 23:59

Dates are defined individually per patient. If more than one date is associated with a specific visit, measurements associated with a specific date are assigned to a study analysis phase according to the rules specified in the table. An analysis phase will not extend beyond the start date of the following phase.

 The off-treatment period (i.e. Follow-up phase) only exists if the trial completion date is after the date of end of last infusion or injection + 112 days.

The post-flare treatment period only applies to those patients who are administered a disease flare treatment with spesolimab. Assessments done on the same day as the first disease flare treatment dose will be assigned to a study analysis phase based on assessment via date and time. If time is not collected for a particular assessment, then assignment will be to the previous study analysis phase, i.e. to the pre-flare treatment period.

### **Overall Maintenance Treatment Period**

The overall maintenance treatment period applies to all patients taking at least one dose of maintenance treatment regardless of flare occurrence. This period will be considered to understand long-term efficacy and safety of spesolimab.

Table 6.1: 4 Flow chart of analysis phases for overall maintenance treatment period

Study analysis phase	Description	Start (included)	End (included)
Screening  phase	Screening	Earliest of (Date of informed consent, first screening procedure)	Date/time of injection of first maintenance study drug minus 1 minute
Maintenance treatment phase & Residual effects period	Maintenance on-treatment period	Date/time of injection of first maintenance study drug (Day 1 for maintenance)	Date of end of (infusion or injection) of last administered spesolimab + 112 days at 23:59
Follow-up  phase	Off-treatment period	Date of end of (infusion or injection) of last administered spesolimab + 113 days at 12:00 a.m.	Latest of: i) Date of End-of-Study visit; ii) last contact date on End of Study page at 23:59

Dates are defined individually per patient. If more than one date is associated with a specific visit, measurements associated with a specific date are assigned to a study analysis phase according to the rules specified in the table. An analysis phase will not extend beyond the start date of the following phase.

 The off-treatment period (i.e. Follow-up phase) only exists if the trial completion date is after the date of end of last injection or infusion + 112 days.

 The screening phase does not exist for re-induction treated patients who subsequently receive maintenance treatment.

### **Disease Flare Treatment Period**

The analysis phase as described below is applicable to both the efficacy and safety analyses of the disease flare treatment period.

The following phases will be used for assessment on the efficacy and AE safety profile only in patients who take disease flare treatment with 1200 mg spesolimab single i.v. infusion. This analysis phase considers the fixed 12-week duration after administration of a disease flare spesolimab infusion up to the time of the planned endoscopy measurement (Rx-Week 12 defined in [Table 6.7: 3](#)).

Table 6.1: 5 Flow chart of analysis phases for disease flare treatment period

Study analysis phase	Description	Start (included)	End (included)
Disease flare treatment phase*	On-treatment period after flare infusion with spesolimab	Date/time of start of infusion of flare treatment (Day 1 for flare treatment)	Date of end of infusion of flare treatment + 98 days at 23:59

Dates are defined individually per patient. If more than one date is associated with a specific visit, measurements associated with a specific date are assigned to a study analysis phase according to the rules specified in the table. An analysis phase will not extend beyond the start date of the following phase.

\*One patient may have multiple disease flare treatment phases if multiple flares happen at different times.

The disease flare treatment period only applies to those patients who are administered a disease flare treatment with spesolimab. Assessments done on the same day as the first disease flare treatment dose will be assigned to a study analysis phase based on assessment via date and time. If time is not collected for a particular assessment, then assignment will be

to the previous study analysis phase, i.e. to the pre-flare treatment period for first administration of disease flare treatment, or to the post-flare treatment period for subsequent administrations.

The selection of data for presentation in this analysis is described in Tables about time window in [Section 6.7](#). Treatments will be labelled as follows:

- “Re-induction Speso 1200 mg IV q4w” [applicable to the re-induction period]  
Selected tables also by prior parent trial treatment
- “Pre-Flare SC” [applicable to the pre-flare treatment period, i.e., censoring data after intake of first flare treatment, including also the old dosing schedule]
- “Post-Flare IV/SC” [applicable to the post flare treatment period, includes also the old dosing schedule]
- “Overall Maintenance” [applicable to the whole period after maintenance treatment, includes also the old dosing schedule]  
Selected tables also by prior parent trial treatment
- “Disease Flare Speso 1200 mg IV SD” [applicable to the disease flare treatment period]  
Selected tables also by prior parent trial treatment

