13. For patients who discontinue study medication before scheduled end of treatment, an early EOT visit has to be scheduled. subsequently EOS visit 16 weeks after last dose of study medication has to be performed.
14. At visit R4 patient response status to i.v. re-induction has to be checked. Sigmoidoscopy and eDiary data review are part of eligibility check to continue into maintenance treatment. Patients who did not respond to i.v. re-induction will be discontinued from study medication and early EOT visit has to be performed. EOS visit has to be performed 16 weeks after last dose of study medication (16 weeks after R3 visit). Sigmoidoscopy does not need to be done at EOT visit for these patients.
15. Visit M1 ([flowchart](#) for re-induction non-responders) has to be performed after results of sigmoidoscopy performed at visit R4 are received (usually 5-7 days)
16. For patients with disease flares only, sigmoidoscopy does not need to be repeated if done within 6 weeks prior to EOT visit.
17. Patients who develop a disease flare during maintenance study treatment period confirmed by sigmoidoscopy will receive a single infusion of 1200mg BI 655130 (SPESOLIMAB) i.v. followed 6 weeks later by intensified maintenance treatment with 600mg BI 655130 s.c. q6w until the originally scheduled EOT visit (i.e. at week 336 after start of first sc. maintenance treatment)
18. Cycle of visits F1-x to F4-x (visits every 6 weeks) is repeated until originally scheduled EOT, 336 weeks after initial visit M1, is reached.
19. QuantiFERON-TB test should be done every 48 wks.

TABLE OF CONTENTS

TITLE PAGE	1
CLINICAL TRIAL PROTOCOL SYNOPSIS	2
FLOW CHART 1A: INDUCTION RESPONDERS V1, V1A, M1-M5B	4
FLOW CHART 1B: INDUCTION RESPONDERS M6-EOS.....	5
FLOW CHART 2: INDUCTION NON-RESPONDERS	6
FLOW CHART 3: PATIENTS WITH DISEASE FLARE.....	7
TABLE OF CONTENTS	10
ABBREVIATIONS	14
1. INTRODUCTION.....	18
1.1 MEDICAL BACKGROUND	18
1.2 DRUG PROFILE	18
1.3 RATIONALE FOR PERFORMING THE TRIAL	20
1.4 BENEFIT - RISK ASSESSMENT.....	21
2. TRIAL OBJECTIVES AND ENDPOINTS.....	34
2.1 MAIN OBJECTIVES, PRIMARY AND SECONDARY ENDPOINTS.....	34
2.1.1 Main objectives.....	35
2.1.2 Primary endpoint(s).....	36
2.1.3 Secondary endpoint.....	36
2.2 Secondary endpoints.....	36
2.3 Other endpoints.....	36
3. DESCRIPTION OF DESIGN AND TRIAL POPULATION	38
3.1 OVERALL TRIAL DESIGN AND PLAN	38
3.2 DISCUSSION OF TRIAL DESIGN, INCLUDING THE CHOICE OF CONTROL GROUP(S)	41
3.3 SELECTION OF TRIAL POPULATION	42

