5.2.5 Other safety parameters

Local tolerability at the administration site of the subcutaneous injection will be assessed by the investigator at the specified visits as noted in the [Flow Chart](#) see [section 4.1.1](#) for further details. Any observed local tolerability reactions like “swelling”, “induration”, “heat”, “redness”, “pain”, or any other findings should be reported as an adverse event in the eCRF. In case of an infusion reaction monitor the patient per standard of care, grade the intensity of the reaction according to RCTC grading (cf. ISF) and proceed as described in [section 4.2.2.1](#). Also draw plasma sample for IgE and ADA (anti-drug antibodies), as detailed in the CTP [section 5.2.3](#) and the lab manual. Assessment according to RCTC implies also reporting as AE.

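### The 98-day flare period is labelled as a single 1200 mg i.v. dose, although s.c. doses fall due within it on Days 43 and 85

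*SAP*

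**What the plan says.** SAP 6.1 (Disease Flare Treatment Period) defines a phase that starts at the flare infusion. Its end in Table 6.1: 5 is "Date of end of infusion of flare treatment + 98 days at 23:59". Its scope is wide: "The analysis phase as described below is applicable to both the efficacy and safety analyses of the disease flare treatment period". The introductory text gives a different length: "This analysis phase considers the fixed 12-week duration after administration of a disease flare spesolimab infusion". The treatment label for all output from this phase is "Disease Flare Speso 1200 mg IV SD". The neighbouring label for the post-flare period names both routes, i.v. and s.c.

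Footnote 17 to the protocol flow charts says that the flare infusion is "followed 6 weeks later by intensified maintenance treatment with 600mg BI 655130 s.c. q6w". SAP 6.1 adds that patients who entered under protocol version 4.0 or earlier may have had 300 mg at that interval.

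SAP Table 6.3: 1 assigns the disease flare period to exposure, adverse events, laboratory, vital signs and the further endpoints defined for it. SAP 7.8 adds the standard safety tables for each flare occurrence. Protocol 5.2.5 requires local injection reactions such as swelling, redness, pain "or any other findings should be reported as an adverse event in the eCRF".

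**The concern.** A reader of a table with this heading would take its events and responses to be those seen after one infusion. For more than half of the window the patient has also had at least one s.c. dose. Injection-site reactions to the post-flare s.c. doses would be tabulated under a single i.v. dose, and the week-12 response would be credited to the infusion alone.

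The SAP treats a similar sequence differently. Where i.v. re-induction is followed by s.c. maintenance, Table 6.1: 1 ends the i.v. phase one minute before the first injection. The interim outputs are meant for regulatory interactions, investigator brochure updates and publications (SAP 3), where a table may be read without Table 6.1: 5 beside it.

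**Working it through.** **Inputs**

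- Infusion on Day 1; phase ends at infusion + 98 days (SAP Table 6.1: 5).
- First s.c. dose 6 weeks after the infusion, then every 6 weeks (protocol flow-chart footnote 17; 6-weekly visits in footnote 18).
- Visit windows of ±7 days around Days 43 and 85; extended window for flare week 12 is Days 65 to 99 (SAP Table 6.7: 3).
- Relative s.c. bioavailability about 70% (protocol 4.1.2); half-life 4 to 5 weeks (protocol 4.1.2, healthy volunteers).

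**Step 1: the plan's own figure.** 1 + 98 = Day 99, which matches the end of the extended flare week-12 window. 98/7 = 14 weeks, not the 12 weeks in the text.

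**Step 2: s.c. doses inside the window.** Days 1 + 42k give 43, 85 and 127. The first two are inside Days 1 to 99 and the third is outside. At the limits of the visit windows (Days 36 to 50 and 78 to 92) the first two remain inside.

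**Step 3: share of the window on or after the first s.c. dose.**

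| First s.c. dose | Days on or after it | Share of 99 days |
|---|---|---|
| Day 36 | 99 − 36 + 1 = 64 | 64.6% |
| Day 43 (planned) | 99 − 43 + 1 = 57 | 57.6% |
| Day 50 | 99 − 50 + 1 = 50 | 50.5% |

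On or after the second planned dose: 99 − 85 + 1 = 15 days, 15/99 = 15.2%. If the phase stopped at Day 85, as the 12-week wording suggests, the share after the first s.c. dose would still be (85 − 43 + 1)/85 = 43/85 = 50.6%.

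**Step 4: does any rule stop the phase earlier?** SAP 6.1 cuts a phase at the start of the next one. The post-flare period starts at the first flare infusion itself (Table 6.1: 3), not at the first s.c. dose, so it does not shorten this phase. SAP 7.8.1 counts time at risk from the i.v. flare dose and censors at the end of the Section 6.1 period. Neither refers to the first s.c. dose.

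**Step 5: the week-12 response.** Protocol 6.2.2 puts sigmoidoscopy before same-day dosing, so on schedule only the week-6 dose precedes the response. In i.v.-equivalent terms that dose is 0.7 × 600 = 420 mg, and 420/(1200 + 420) = 25.9% of the two doses together. For 300 mg it is 0.7 × 300 = 210 mg, and 210/(1200 + 210) = 14.9%.

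As an illustration only, assume mono-exponential decay, ignoring absorption time and drug left from earlier maintenance. At week 12 the remaining amounts are:

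- Half-life 4 weeks: 1200 × 0.5^(12/4) = 150.0 mg from the infusion and 420 × 0.5^(6/4) = 148.5 mg from the s.c. dose, a share of 49.7% (33.1% for 300 mg).
- Half-life 5 weeks: 227.4 mg and 182.8 mg, a share of 44.6% (28.7% for 300 mg).

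**The case against.** The strongest reply is that the label names the index dose, not everything given in the window. Protocol Table 4.1.1: 1 and the definition of the flare-treatment set in SAP 6.3 use the same single-dose term, and SAP 6.1 itself says that s.c. dosing follows. The window is anchored on the infusion and runs to the week-12 check that protocol 3.1 uses to judge response to flare treatment. This stands in part. A careful reader of SAP 6.1 can work out the regimen; a reader of one table cannot.

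It follows that a reader should not infer that the period was designed to isolate the infusion and fails at its purpose. The SAP never states that aim. Nor are Days 1 to 42 free of s.c. drug. Flares arise during s.c. maintenance, and on the same decay assumption a dose given 4 weeks before the infusion still has 0.5^(4/4) = 50% to 0.5^(4/5) = 57% of its amount left on the infusion day. A cut at the first post-flare s.c. dose is therefore not a clean i.v. period. It would also lose delayed events, which the SAP's 112-day residual effect period elsewhere counts as on-treatment.

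Two further limits hold. The same events also appear under the post-flare and overall maintenance periods, and injection-site reactions can be recognised by preferred term. Flow Chart 3 and the SAP sections on further endpoints are not in the public text, so the titles and footnotes of the flare-efficacy displays cannot be checked.

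**Conclusion.** The label misattributes. On the planned schedule 58% of the window (51% to 65% across the visit window) follows at least one s.c. dose, and the week-12 response follows the week-6 dose. This rests on footnotes 17 and 18 for dose timing and on patients staying on treatment. Patients withdrawn before week 6 are unaffected, and non-responders withdrawn at week 12 may not receive the second dose.

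Two stronger conclusions might be drawn, and the documents support neither. One is that both s.c. doses, 840 mg i.v.-equivalent or 840/(1200 + 840) = 41% of the total, bear on the week-12 response. On schedule the second dose comes after the endoscopy. It matters for events on Days 85 to 99, and for response only if the endoscopy is late within the extended window. The other is that results are miscalculated. Counts and rates for the period are correctly defined, all analyses are descriptive, the primary endpoint is summarised for maintenance, and the secondary endpoint uses the overall maintenance period. The error lies in what the heading says the patients received.

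**What to change.** 1. In SAP 6.1 and Table 6.1: 5, relabel the period and its week-12 display as 1200 mg i.v. followed by s.c. q6w, with a note that some patients had 300 mg s.c. under the old schedule. At the same time reconcile the stated 12-week duration with + 98 days.
2. Beside the 98-day tables, add one adverse event summary, with matching time at risk in SAP 7.8.1, ending the day before the first post-flare s.c. dose or at + 98 days if that is earlier. A cut at the minute will not work: SAP 7.8.1 says only the start date of an event is collected. A footnote to Table 6.1: 1 presupposes event times, but a day-level rule works either way. Title the summary as the time before the first post-flare s.c. dose, not as i.v. only.

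The cost is SAP wording and one extra table from dose dates that are already recorded. The supplementary window is only about 6 weeks, so it will hold fewer events and miss delayed ones. It should supplement the 98-day version, not replace it. Nothing here bears on the dosing itself.
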